15.1 RESEARCH PARTICIPANT REGISTRATION AND RANDOMIZATION PROCEDURES

15.2 Research Participant Registration

Confirm eligibility as defined in the section entitled Inclusion/Exclusion Criteria.

Obtain informed consent, by following procedures defined in section entitled Informed Consent Procedures.

During the registration process registering individuals will be required to complete a protocol specific Eligibility Checklist.

The individual signing the Eligibility Checklist is confirming whether or not the participant is eligible to enroll in the study. Study staff are responsible for ensuring that all institutional requirements necessary to enroll a participant to the study have been completed. See related Clinical Research Policy and Procedure #401 (Protocol Participant Registration).

15.3 Randomization

There will be no randomization in this study.

16.1 DAT A MANAGEMENT ISSUES

A Research Study Assistant (RSA) will be assigned to the study. The responsibilities of the RSA include project compliance, data collection, abstraction and entry, data reporting, regulatory monitoring, problem resolution and prioritization, and coordinate the activities of the protocol study team.

The data collected for this study will be entered into a secure database (CRDB). Source documentation will be available to support the computerized patient record.

16.2 Quality Assurance

Registration reports will be generated to monitor patient accruals and completeness of registration data. Routine data quality reports will be generated to assess missing data and inconsistencies. Accrual rates and extent and accuracy of evaluations and follow-up will be monitored periodically throughout the study period and potential problems will be brought to the attention of the study team for discussion and action

Random-sample data quality and protocol compliance audits will be conducted by the study team, at a minimum of two times per year, more frequently if indicated.

16.3 Data and Safety Monitoring

The Data and Safety Monitoring (DSM) Plans at Memorial Sloan-Kettering Cancer Center were approved by the National Cancer Institute in September 2001. The plans address the new policies set forth by the NCI in the document entitled "Policy of the National Cancer Institute for Data and Safety Monitoring of Clinical Trials" which can be found at: <http://cancertrials.nci.nih.gov/researchers/dsm/index.html>. The DSM Plans at MSKCC were established and are monitored by the Office of Clinical Research. The MSKCC Data and Safety Monitoring Plans can be found on the MSKCC Intranet at: <http://mskweb2.mskcc.org/irb/index.htm>

There are several different mechanisms by which clinical trials are monitored for data, safety and quality. There are institutional processes in place for quality assurance (e.g., protocol monitoring, compliance and data verification audits, therapeutic response, and staff education on clinical research QA) and departmental procedures for quality control, plus there are two institutional committees that are responsible for monitoring the activities of our clinical trials programs. The committees: *Data and Safety Monitoring Committee (DSMC)* for

Phase I and II clinical trials, and the *Data and Safety Monitoring Board (DSMB)* for Phase III clinical trials, report to the Center's Research Council and Institutional Review Board.

During the protocol development and review process, each protocol will be assessed for its level of risk and degree of monitoring required. Every type of protocol (e.g., NIH sponsored, in-house sponsored, industrial sponsored, NCI cooperative group, etc.) will be addressed and the monitoring procedures will be established at the time of protocol activation.

17.1 PROTECTION OF HUMAN SUBJECTS

Prior to the enrollment of each patient, the risks, benefits and objectives of the study will be reviewed with the participant, including a discussion of the possible toxicities and side effects.

Risks: Potential risks to the patient include pain and discomfort related to phlebotomy and related to time spent undergoing [¹⁸F] FLT PET and MR scanning. Specific toxicities and side effects related to [¹⁸F] FLT PET imaging and MR imaging including radiation exposure are described in section 11.

Benefits: We do not expect patients to derive any clinical benefit from this clinical trial. We hope in the future that knowledge from this trial will help evaluating treatment response in future patients with metastatic breast cancer to the brain treated with WBRT or WBRT in combination with sorafenib, in better distinguishing tumor progression from radionecrosis.

Alternative, non-protocol options will be discussed with the patient. It will be reviewed that participation in this clinical trial is voluntary and that the patient may withdraw consent at any time. The financial costs of the study will be discussed; FLT PET scans and blood draw for PK analysis will be done free of charge.

17.2 Privacy

MSKCC's Privacy Office may allow the use and disclosure of protected health information pursuant to a completed and signed Research Authorization form. The use and disclosure of protected health information will be limited to the individuals described in the Research Authorization form. A Research Authorization form must be completed by the Principal Investigator and approved by the IRB and Privacy Board (IRB/PB).

17.3 Serious Adverse Event (SAE) Reporting

An adverse event is considered serious if it results in ANY of the following outcomes:

- Death
- A life-threatening adverse event
- An adverse event that results in inpatient hospitalization or prolongation of existing hospitalization
- A persistent or significant incapacity or substantial disruption of the ability to conduct normal life functions
- A congenital anomaly/birth defect

- Important Medical Events (IME) that may not result in death, be life threatening, or require hospitalization may be considered serious when, based upon medical judgment, they may jeopardize the patient or subject and may require medical or surgical intervention to prevent one of the outcomes listed in this definition

Note: Hospital admission for a planned procedure/disease treatment is not considered an SAE.

SAE reporting is required as soon as the participant signs consent. SAE reporting is required for 30-days after the participant's last investigational treatment or intervention. Any events that occur after the 30-day period and that are at least possibly related to protocol treatment must be reported.

If an SAE requires submission to the IRB office per IRB SOP RR-408 „Reporting of Serious Adverse Events“, the SAE report must be sent to the IRB within 5 calendar days of the event. The IRB requires a Clinical Research Database (CRDB) SAE report be submitted electronically to the SAE Office as follows:

Reports that include a Grade 5 SAE should be sent to [contact]. All other reports should be sent to [contact].

The report should contain the following information:

Fields populated from CRDB:

- Subject's initials
- Medical record number
- Disease/histology (if applicable)
- Protocol number and title

Data needing to be entered:

- The date the adverse event occurred
- The adverse event
- The grade of the event
- Relationship of the adverse event to the treatment (drug, device, or intervention)
- If the AE was expected
- The severity of the AE
- The intervention
- Detailed text that includes the following
 - A explanation of how the AE was handled
 - A description of the subject's condition
 - Indication if the subject remains on the study
- If an amendment will need to be made to the protocol and/or consent form
- If the SAE is an Unanticipated Problem

The PI's signature and the date it was signed are required on the completed report.

The CRDB SAE report should be completed as per above instructions. If appropriate, the report will be forwarded to the FDA by the SAE staff through the IND Office

18.1 INFORMED CONSENT PROCEDURES

Before protocol-specified procedures are carried out, consenting professionals will explain full details of the protocol and study procedures as well as the risks involved to participants prior to their inclusion in the study. Participants will also be informed that they are free to withdraw from the study at any time. All participants must sign an IRB/PB-approved consent form indicating their consent to participate. This consent form meets the requirements of the Code of Federal Regulations and the Institutional Review Board/Privacy Board of this Center. The consent form will include the following:

1. The nature and objectives, potential risks and benefits of the intended study.
2. The length of study and the likely follow-up required.
3. Alternatives to the proposed study. (This will include available standard and investigational therapies. In addition, patients will be offered an option of supportive care for therapeutic studies.)
4. The name of the investigator(s) responsible for the protocol.
5. The right of the participant to accept or refuse study interventions/interactions and to withdraw from participation at any time.

Before any protocol-specific procedures can be carried out, the consenting professional will fully explain the aspects of patient privacy concerning research specific information. In addition to signing the IRB Informed Consent, all patients must agree to the Research Authorization component of the informed consent form.

Each participant and consenting professional will sign the consent form. The participant must receive a copy of the signed informed consent form.

20.0 APPENDICES

APPENDIX A: Study calendar

APPENDIX B: Performance codes status

APPENDIX A

Study Calendar

Tests	Screening	7-10 days after WBRT	10-12 weeks after WBRT
MRI Brain ¹	X		X
FLT-PET ¹	X	X	X
FLT PK Blood draw ²	X	X	X
History and Physical examination ³	X		
CBC, CMP ³	X		
Pregnancy test ³	X		

¹MRI and FLT-PET will all be done within 4 weeks prior to initiation of WBRT. MRI will be done within one week before the FLT-PET scan.

² PK Blood draw will be done 60 min (+ 10 min window) after FLT injection

³ Blood tests will be done within 1 week of initiation of WBRT

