6.1 CRITERIA FOR SUBJECT ELIGIBILITY

6.2 Subject Inclusion Criteria

- Histologically-confirmed (confirmation done at MSKCC) metastatic adenocarcinoma of the breast
- Radiologic evidence of new and/or progressive brain metastases (≥ 10 mm in longest dimension) by MRI imaging of the Brain
- Planned WBRT based on number (≥ 3 lesions) and/or size (≥ 1 cm) of brain metastases.
- Age ≥ 18 years; males and females
- Patients who require additional clinically indicated stereotactic radiosurgery (SRS) in addition to WBRT will also be eligible.
- Life expectancy of >12 weeks.
- Karnofsky Performance Status (KPS) $\geq 70\%$.
- Creatinine ≤ 2.0 times the upper limit of normal.
- Women of childbearing potential must have a negative serum pregnancy test performed within 7 days prior to enrollment, must be non-lactating and must agree to use adequate contraception prior to enrollment and for the duration of study participation.
- No limit to prior therapies with last anti-cancer treatment ≥ 2 weeks from initiation of WBRT. Please note: there is no washout period required for trastuzumab, pertuzumab for patients who have developed new parenchymal brain metastases while on these agents.

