8.0 PRETREATMENT EVALUATION

- MR Brain will be obtained within 4 weeks prior to initiation of WBRT to ensure evidence of new/progressive brain metastases. MR imaging will include images before and after the administration of gadolinium-diethylenetriamine - pentaacetic acid (Gd-DTPA).
- FLT-PET will be obtained within 4 weeks prior to initiation of WBRT and within 2 weeks of the MR Brain. History and physical Examination within 1 week prior to initiation of WBRT.
- Patients will also undergo CBC, comprehensive metabolic panel within 1 week prior to initiation of WBRT.
- Women with childbearing potential will also undergo a serum pregnancy test. See Appendix A for study calendar.

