9.2.2 FLT PET scanning

Following scout view, a low dose CT (80mA) of the brain will be obtained for an anatomic localization and attenuation correction. Following intravenous injection of $[^{18}\text{F}]$ FLT, dynamic PET emission data of the brain will be obtained for up to 60 min to obtain kinetic information on tumor uptake for modeling. Image acquisition shall start immediately after injection using the following sequence: 4 frames of 15 seconds, 4 frames of 30sec, 7 frames of 1-minute, then 10 frames of 5-minutes, i.e. for a full scan duration of 60-minutes. After the 60 minutes dynamic scan, if the patient is capable and willing, an additional 10 minute static acquisition will be acquired at 90 minutes. Dynamic FLT scans will be using standard clinical protocol. Patients may take a break and get off the table, for instance for bathroom break before the additional 10 minute static acquisition.

FLT PET scans will be obtained at baseline (within 4 weeks of WBRT and within 2 week after MR imaging), 7-10 days after WBRT and 10-12 weeks after WBRT.

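### Neither pregnancy-test window is tied to the baseline FLT injection, so the entry test's age at the first research radiation exposure is limited only indirectly

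*Combined protocol and SAP*

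**What the plan says.** The timing of the pregnancy test is set in three places.

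- Section 6.2 makes it an entry condition: women of childbearing potential "must have a negative serum pregnancy test performed within 7 days prior to enrollment". The same criterion says that they "must agree to use adequate contraception prior to enrollment and for the duration of study participation".
- Section 8.0 gives no window of its own and refers to the calendar: "Women with childbearing potential will also undergo a serum pregnancy test. See Appendix A for study calendar". The neighbouring items in that section (history and physical, CBC, metabolic panel) do have a stated window of 1 week before WBRT.
- Appendix A has one mark for the pregnancy test, in the screening column. Its footnote 3 reads "Blood tests will be done within 1 week of initiation of WBRT".

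The baseline imaging windows are counted from WBRT and from the MRI. Section 8.0 says "FLT-PET will be obtained within 4 weeks prior to initiation of WBRT and within 2 weeks of the MR Brain". Section 9.2.2 gives the order: "within 4 weeks of WBRT and within 2 week after MR imaging". Sections 9.3 and 10.2 also allow 2 weeks between the scans. The schema note in section 1.0 and Appendix A footnote 1 allow only one week from MRI to FLT-PET.

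**The concern.** The first research radiation exposure in this study is the baseline FLT-PET/CT: up to 10 mCi of FLT (section 9.2.1) plus a low-dose CT (section 9.2.2). Section 9.3 calls it a research scan, and section 17.1 expects no clinical benefit from taking part. A pregnancy test meant to protect against that exposure should be recent when the tracer is injected. The protocol chose 7 days as its standard of recency but counts those days from enrolment in one place and from WBRT in another.

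A site that works from the calendar could schedule the test around WBRT and find that its window opens after the FLT injection. A site that works from section 6.2 will have a test before FLT, but nothing in the pregnancy-test wording says how old it may be by then. The stake is the timing of a safety check. No response measure or analysis depends on it.

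**Working it through.** The documents state no figure for the age of the test at injection, so there is none to reproduce. The check derives the limits that the written windows imply.

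**Inputs.** Day 0 is the start of WBRT. T = entry test, E = enrolment, M = baseline MRI, F = baseline FLT injection.

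- E − 7 ≤ T ≤ E (section 6.2).
- M and F lie between day −28 and day 0 (section 8.0, Appendix A footnote 1).
- 0 ≤ F − M ≤ g, with g = 14 (sections 8.0, 9.2.2, 9.3, 10.2) or g = 7 (section 1.0 schema note, Appendix A footnote 1).
- The footnote 3 window is day −7 to day 0, reading it as before WBRT.
- E ≤ F. This is inferred: eligibility is confirmed at registration (section 15.2), and a negative baseline FLT-PET takes the patient off study (sections 4.2 and 13.0).
- M ≤ E. This is also inferred, and holds if the eligibility MRI is the baseline MRI. Section 6.2 requires "Radiologic evidence of new and/or progressive brain metastases" and section 8.0 says "MR Brain will be obtained within 4 weeks prior to initiation of WBRT to ensure evidence of new/progressive brain metastases", but no section says that they are the same scan.

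**Step 1: footnote 3 against the injection.** If F is earlier than day −7, every day of the footnote 3 window is later than F. With FLT on day −28, that window falls 28 − 7 = 21 to 28 days after the injection.

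**Step 2: can one test meet both rules?** T ≤ E ≤ F. If F is earlier than day −7, so is T, and T lies outside the footnote 3 window. One test can meet both rules only if FLT is on day −7 or later.

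**Step 3: maximum age of the entry test at injection.** F − T = (F − E) + (E − T) ≤ (F − M) + 7 ≤ g + 7.

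**Step 4: test drawn on or after the MRI.** Then T ≥ M, so F − T ≤ F − M ≤ g.

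**Step 5: one test meets both rules.** Then T ≥ −7 and F ≤ 0, so F − T ≤ 7 (6 if FLT is on day −1 at the latest).

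| Reading | 1-week gap | 2-week gap | Schedule that reaches the limit |
|---|---|---|---|
| Test may precede the MRI | 7 + 7 = 14 days | 7 + 14 = 21 days | Test −35; MRI and enrolment −28; FLT −21 or −14 |
| Test on or after the MRI | 7 days | 14 days | Test, MRI and enrolment −28; FLT −21 or −14 |
| One test meets both rules | 7 days | 7 days | Test and enrolment −7; FLT 0 |

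In the first two rows FLT precedes day −7, so a test in the footnote 3 window cannot update the result before injection. If 4 weeks is read as fewer than 28 days, the dates in those rows move by one day and the maxima do not change.

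**The case against.** The strongest reply is that the protocol already covers this. Section 6.2 puts a negative serum test before enrolment, hence before FLT, and contraception is required by sections 6.2 and 11.0. That stands, and it is why the point is minor.

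A second reply is that the 14-day and 21-day schedules are corner cases, because the test is drawn a week before the MRI that shows the qualifying metastases. That also stands. In the more natural order the limits are 7 and 14 days, and with the 1-week gap the test is already within the protocol's own 7 days.

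A third is that the calendar shows one test, so one test should meet both rules and would be at most 7 days old. The reading is possible, and a narrower FLT schedule would not breach a 4-week outer limit. But it would confine FLT to the last week before WBRT for these women, and nothing in the text says so.

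A fourth is that FLT is injected again at 7–10 days and at 10–12 weeks after WBRT with no pregnancy test in the calendar, so fixing only the first injection looks arbitrary. Contraception is the stated safeguard there. The baseline injection differs in that an existing test is being timed against the wrong event.

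Cohort 1 is also on a separate phase I trial whose testing schedule is not in these documents, so the practical gap for that cohort cannot be judged.

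**Conclusion.** The point holds as a minor safety and scheduling matter. The calendar times the pregnancy test by WBRT although the first research exposure is the FLT injection, which can come up to 4 weeks earlier. For any FLT more than 7 days before WBRT, the calendar window misses the injection and the two rules cannot be met by one test. The derived maximum age of the entry test is 14 or 21 days, 7 or 14 days if it is drawn on or after the MRI, and 7 days if one test serves both rules. The first two pairs assume that the eligibility MRI is the baseline MRI; all three assume that enrolment precedes FLT.

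Three stronger readings are not supported. A reader might infer that FLT can be given with no prior pregnancy test; section 6.2 rules that out. A reader might take 14 to 21 days as the usual age; these are conditional maxima, and many permitted schedules give a fresher test. A reader might conclude that the age is unlimited; that needs a separate eligibility MRI, whereas section 8.0 describes the baseline MRI in nearly the terms of the inclusion criterion. The number of women affected and any fetal dose cannot be estimated from the documents. No endpoint or analysis is affected.

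**What to change.** In sections 6.2 and 8.0 and in Appendix A footnote 3, require a negative serum pregnancy test before enrolment and within 7 days before the first FLT injection, with one test allowed to serve both. The clinical team should confirm the 7 days. Either remove the pregnancy-test row from footnote 3 or state that a test near WBRT is additional. The test would then be at most 7 days old at the first injection under every reading above. The cost is wording in three places, plus a moved or, for some women, repeated blood draw.

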APPENDIX B

Description: Karnofsky Scale	Karnofsky Scale (%)
No complaints; no evidence of disease. Able to carry on normal activity.	100
Minor signs or symptoms of disease.	90
Some signs or symptoms of disease with effort; cares for self.	80
Unable to carry on normal activity or to do active work.	70
Requires occasional assistance but is able to care for most personal needs.	60
Requires considerable assistance and frequent medical care.	50
Disabled; requires special care and assistance.	40
Severely disabled; hospitalization indicated, although death not imminent.	30
Very sick; hospitalization necessary; requires active support.	20
Moribund; fatal processes progressing rapidly.	10
Dead	0
